9.3.2 ANALYSIS OF THE PRIMARY EFFICACY ENDPOINT(S)

The efficacy primary endpoint of the study is the maximum clinical severity of disease as assessed by the clinical status ordinal scale. The primary efficacy analysis will be performed using a proportional odds model. This model allows comparing odds ratios on ordinal categories between the experimental treatment and the placebo via a set of regression parameters. The statistical significance of regression parameters will be tested using a one-sided test for the superior efficacy by telmisartan. Alternatively, several ordinal categories can be combined to obtain a composite binary class outcome, in case of insufficient class representations observed. In this situation, group comparison with respect to a binary outcome can be performed using the logistic regression model.

In addition to the primary analysis, longitudinal outcomes obtained at baseline (day 1), days 4, 10, and 21 will be used in a generalized mixed-effect regression model (i.e., cumulative link mixed model) that contains treatment and days, and treatment: days interaction as fixed effects. In the model, treatment: days interaction represents the difference in longitudinal trajectories between the two treatment groups. The statistical significance of interactions will be determined. The regression models used for analysis can be further adjusted for any unbalanced covariates observed at baseline.

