9.3 DESCRIPTION OF STATISTICAL METHODS

9.3.1 GENERAL APPROACH

This is a prospective, randomized, double-blind 3-week study of telmisartan vs placebo in symptomatic individuals diagnosed with COVID-19 disease. Subjects will be randomized 1:1 to receive telmisartan vs placebo for 3 weeks (21 days). A block randomization will be applied to ensure the balance of participant numbers and baseline severity between treatments.

The baseline characteristics of participants will be summarized by descriptive statistics and compared between the two groups to check any imbalance. The primary efficacy endpoint for the study is an ordinal outcome corresponding to the maximum clinical status of the study subject. The proportional odds model and logistic regression techniques will be applied to compare the ordinal outcome between treatments, based on odds ratios. There are several secondary efficacy endpoints defined for the study. For those measures, averages and rates will be compared between groups, appropriately. Longitudinal mixed-effects models will be utilized to handle longitudinal outcome measures observed at days 1, 4, 10, and 21. The covariate use in regression models will be limited due to the relatively small sample size. Tests of normality will be performed on continuous data and transformation applied where applicable. Type-I error for hypothesis tests will be fixed at 5% nominal level. All efficacy and safety estimates (e.g.

average and proportions) will be provided with 95% confidence intervals (95% CI). The multiplicity error in exploratory analyses will be corrected via the false discovery rate. All efforts will be taken to minimize loss-to-follow-up. However, small amounts of missing data may occur. In such cases, participants without final outcome data will be excluded from the analysis. Sensitivity analysis with multiple imputations will be performed for confirming results. Statistical analyses will be performed using the R software 3.5.1 version.

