9.3.3 ANALYSIS OF THE SECONDARY ENDPOINT(S)

Secondary efficacy endpoints for the study are given by a set of continuous/count measures observed at days 4, 10 and 21 (i.e., components of the RAS and blood biomarkers indicative of pro-inflammatory and coagulation disturbances, circulating T cell (CD4 and CD8), NK cell, and monocytes). A shift in distribution location parameter will be tested for the group companion, using two sample t-test or the Wilcoxon rank-sum test selected upon the outcome distributions. Additionally, longitudinal secondary outcomes obtained at baseline (day 1), days 4, 10, and 21 will be analyzed using generalized mixed effect models and together with a proper link function (i.e., identity, log, etc.). In those models, days: treatment interactions, will be tested for the differences in trajectories. Covariate adjustments will be applied if required.

AEs are categorical data. AEs will be summarized as frequencies and percentages within telmisartan and placebo groups. Chi-squared test or Fisher's exact test will be used to test for differences in proportions between two groups.

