9.4 SAMPLE SIZE

The sample size estimation for the proposed study is not provided considering that this is a pilot study. A total sample of 40 participants will be used in the study (20 per group). The above sample size was determined based on the feasibility assessment. Suppose, in the placebo group, the vector of probabilities for observing the ordinal scale outcomes is {0.40, 0.40, 0.05, 0.04, 0.04, 0.04, 0.03}, respectively for categories 1-7. If we assume the corresponding vector for the experimental treatment group as {0.76, 0.18, 0.02, 0.01, 0.01, 0.01}, that will produce an odds ratio of 5.0 between the two groups. In this scenario, we will have about 80% power to detect a treatment difference using the proportional odds model at 5% type-I error. Also, the selected sample size will allow us to detect a standardized effect size of 0.9 at Cohen's d scale, above 80% power, for a mean comparison between two groups via a two-sample T-test for a Gaussian outcome.

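### The supplementary longitudinal models give treatment a free effect at the pre-dose day 1 visit, test only the treatment-by-days interaction, and leave the coding of days unstated; this costs precision but does not bias the trial

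*Combined protocol and SAP*

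**What the plan says.** Section 9.3.2 first specifies the primary analysis, a proportional odds model for maximum clinical severity. As a further analysis it plans a cumulative link mixed model for Clinical Status at days 1, 4, 10 and 21 "that contains treatment and days, and treatment: days interaction as fixed effects". It explains that the "treatment: days interaction represents the difference in longitudinal trajectories between the two treatment groups", and it makes the interaction the term whose significance is assessed.

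Section 9.3.3 plans two-sample t or Wilcoxon tests for the secondary measures at days 4, 10 and 21. It then adds mixed models that again include day 1 among the outcomes: "In those models, days: treatment interactions, will be tested for the differences in trajectories".

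Neither section says whether days is a factor or a number, sets the arms equal at day 1, or names a visit-specific or average contrast. Both allow covariate adjustment, in 9.3.2 for covariates found unbalanced at baseline and in 9.3.3 where needed. Neither names the outcome's own day 1 value.

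Under 6.4.6, the day 1 assessments and blood draw take place at the entry visit, and the participant takes the first dose after returning home. Section 9.3.1 plans block randomisation intended to balance baseline severity.

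**The concern.** Day 1 is pre-dose and the arms are randomised, so the expected arm difference at day 1 is zero. A model with a treatment main effect estimates that difference anyway. The tested interaction then measures each arm's departure from its own observed day 1 mean and carries the full sampling noise of that visit. With 20 per arm this noise matters unless the within-person correlation is high.

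The coding of days matters separately. As a factor, the interaction is three differences in change from day 1. As a number, it is one difference in straight-line slope over 21 days, which is a poor summary of a benefit that appears early and fades as both arms recover. The text permits either coding, and the two can give very different answers from the same data.

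**Working it through.** **Inputs.** 20 per arm (9.4). For alpha, "Type-I error for hypothesis tests will be fixed at 5% nominal level" (9.3.1). The primary model is "tested using a one-sided test for the superior efficacy by telmisartan" (9.3.2); no sidedness is given for the interactions, so two-sided 5% is used. Visits are at days 1, 4, 10 and 21. The illustrative effect is 0.9 SD, the standardised effect in 9.4. The within-person correlation r is not in the documents; it is assumed equal between all visits (compound symmetry) and varied.

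**The plan's own figure.** Section 9.4 says "we will have about 80% power to detect a treatment difference using the proportional odds model at 5% type-I error", for a scenario "that will produce an odds ratio of 5.0 between the two groups". Applying an odds ratio of 5 to the stated placebo probabilities, Whitehead's variance for the log odds ratio is 12/[N(1 − Σm³)], where m is the mean category probability over the arms. With N = 40 and Σm³ = 0.2247, the SE is 0.622 and z = 1.609/0.622 = 2.59. Power is 82.7% one-sided and 73.5% two-sided; simulation gives 80.3% and 69.8%. The stated figure is reproduced one-sided. For d = 0.9, two-sided power is 81.2% (normal) or 79.2% (t). None of these figures concerns the longitudinal models.

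**Single visit, days as a factor.** Relative variance is 2(1 − r) for the change-from-day-1 contrast and 1 − r² when the arms share a day 1 mean. At r = 0.5 these are 1.00 and 0.75.

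**Joint 3-df test.** Let e be the true effects in SD at days 4, 10 and 21. The noncentrality parameters are:

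- Free day 1 effect (as planned): λ = [10/(1 − r)] × [Σe² − (Σe)²/4]
- Shared day 1 mean: λ = [10/(1 − r)] × [Σe² − r(Σe)²/(1 + 3r)]

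For 0.9 SD at all three visits, Σe² = 2.43 and (Σe)² = 7.29. For days 4 and 10 only, Σe² = 1.62 and (Σe)² = 3.24. For a single visit, both are 0.81.

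| Effect | r | λ planned | λ shared | Power planned | Power shared |
|---|---|---|---|---|---|
| Sustained | 0.3 | 8.68 | 18.27 | 69% | 96% |
| Sustained | 0.5 | 12.15 | 19.44 | 85% | 97% |
| Sustained | 0.7 | 20.25 | 26.13 | 98% | 99.5% |
| Days 4 and 10 | 0.5 | 16.20 | 19.44 | 94% | 97% |
| Day 4 or day 10 only | 0.5 | 12.15 | 12.96 | 85% | 87% |

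**Average post-dose effect, r = 0.5.** The variance is (2/20)(4/3)(1 − r) = 0.0667 as planned and (2/20)[(1 + 2r)/3 − r²] = 0.0417 with a shared mean. For a sustained effect, power is 94% against 99%. With the shared mean, power for the average is 84% for days 4 and 10 only (0.6/0.204 = 2.94) and 31% for a single visit (0.3/0.204 = 1.47).

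**Days as a number, free day 1 effect.** The mean day is 9, so the slope weights are −8, −5, +1 and +12, over 234. At r = 0.5 the slope SE is √(0.05/234) = 0.0146.

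- Sustained: 8 × 0.9/234 = 0.0308, z = 2.10, power 56%.
- Days 4 and 10 only: −4 × 0.9/234 = −0.0154, z = −1.05. Rejection is 18%, of which about 0.1 percentage points favour treatment.
- With a shared day 1 mean but days still numeric, power for that transient effect is about 5%, so the constraint alone does not cure the coding.

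**Sensitivity to the correlation structure.** If correlation decays with time (0.5 for a nine-day gap), 3-df power for a sustained effect is 98% planned and above 99% shared. Numeric days then gives 5% for days 4 and 10 only: still blind, but no longer pointing towards harm.

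**Ordinal check.** This is a 200-run simulation of a cumulative link mixed model with five categories, a random intercept, latent correlation of about 0.5 and latent effect 1.8. Monte Carlo error is about 3.5 points (√(0.25/200)).

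| Effect | Factor, planned | Factor, shared | Numeric, planned |
|---|---|---|---|
| None | 5.5% | 5% | 7% |
| Sustained | 55% | 76% | 38% |
| Days 4 and 10 | 71% | 75% | 8% (1.5% favouring treatment) |
| Day 4 only | 58% | 59% | 11% (0% favouring treatment) |

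**The case against.** The strongest reply is that these models decide little. They are added to a primary test that uses maximum severity, counted from day 3 for non-hospitalised participants, and so can register a transient peak. The secondary measures have separate two-sample tests. A reader might infer that the plan judges efficacy by the interaction, or that a real effect would be lost to the whole trial. The documents do not support either reading.

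A reader might also infer that the plan enters days as a number and is therefore blind to transient effects. It does not say so. Four discrete visits, and a plural reference to interactions, fit a factor at least as well. With a factor, the planned test already has 94% power for the days 4 and 10 effect at r = 0.5. Numeric coding is also not always worse: for an effect rising steadily to 0.9 SD at day 21, it gives 87% at r = 0.5 against 74% for the planned factor test.

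It is tempting to test the average post-dose effect instead. For transient effects that is weaker than the planned factor interaction: 84% against 94% for days 4 and 10, and 31% against 85% for a single visit.

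These objections limit the point without removing it. The provision to adjust for unbalanced covariates depends on the data and does not name the outcome's own baseline. The intention to limit covariates in a small sample is no obstacle, because sharing the day 1 mean removes a parameter.

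**Conclusion.** The point holds as a loss of efficiency and an incomplete specification in supplementary analyses. The free day 1 effect is explicit in 9.3.2; 9.3.3 tests the same interaction with day 1 among the outcomes. The analyses that do not use these models are untouched, and there is no bias or type I error problem: the null rejection rates in the simulation are compatible with 5% given its error.

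The size depends on a correlation that the documents do not give. For a sustained 0.9 SD effect the like-for-like gain in 3-df power is about 27 points at r = 0.3, 12 at r = 0.5 and under 2 at r = 0.7. For transient effects with days as a factor it is about 2 to 3 points at r = 0.5. The Gaussian figures treat the covariance as known and only approximate the Clinical Status model, where the simulation shows gains of about 21 points (sustained) and 4 points or less (transient). The larger hazard, a slope that misses or reverses a transient benefit, arises only if days is coded as a number; the reversal also depends on the correlation structure.

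**What to change.** In 9.3.2 and 9.3.3, state:

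- Day is a factor with levels 1, 4, 10 and 21.
- The arms share one mean at day 1; treatment enters only through its interactions with days 4, 10 and 21. Adjusting for the outcome's own day 1 value, with days 4, 10 and 21 as outcomes, is a close alternative but not exactly equivalent in the cumulative link model.
- The test is the joint 3-df test of the three post-dose treatment effects, reported with day-specific effects and 95% CIs.
- The average post-dose effect may be reported as a summary, but does not replace the joint test.

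The coding and the constraint should be changed together, since neither does the other's work. The cost is a few sentences and a different design matrix in the same software, with no new data or visits. The wording should be settled before unblinding.

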4.1.1 PRIMARY ENDPOINT

The primary endpoint is the maximum clinical severity of disease for each participant as assessed on a 7-point **Clinical Status** ordinal scale adapted from the WHO MASTER PROTOCOL for the Treatment of COVID-19 in Hospitalized Patients. The WHO 7-point scale was modified by adding sub-categories for the categories of 'Not hospitalized, limitation on activities' (based on scoring on a **Symptom Scale** to be filled out by participants daily, as explained below), as well as for the 'Hospitalized, requiring supplemental oxygen' and 'Hospitalized, on non-invasive ventilation or high flow oxygen devices' categories. For non-hospitalized participants, the maximum clinical severity recorded for any day \geq day 3 of study will be used. For participants who become hospitalized, the maximum clinical severity prior to discharge will be used.

Clinical Status Classification	Score
Not hospitalized, no limitations on activities	1.0
Not hospitalized, limitation on activities as assessed by the Symptom Scale below	
(a) \leq 3 points	2.0
(b) 4-6 points	2.25
(c) 7-9 points	2.5
(d) 10-12 points	2.75
Hospitalized, not requiring supplemental oxygen;	3.0
Hospitalized, requiring supplemental oxygen:	
(a) Requiring supplemental oxygen at < 6 L/min	4.0
(b) Requiring supplemental oxygen at ≥ 6 L/min	4.5
Hospitalized, on non-invasive ventilation or high flow oxygen devices	
(a) Non rebreather mask	5.0
(b) Noninvasive ventilation (NIV), high flow O ₂ devices	5.5
Hospitalized, on invasive mechanical ventilation or ECMO	6.0
Death	7.0

'**Symptom Scale**' to be used for sub-classification of the 'Not hospitalized, limitation on activities' category on the modified WHO 7-point ordinal scale is as shown below. The participant will be asked to daily grade each symptom by severity to obtain a total score. For example, the assessment of grade 2 fever (2 points), grade 1 breathing (1 point) and grade 3 fatigue (3 points) will result in a total score on the symptom scale of 6 for that day. Referring back to the **Clinical Status** classification above, the clinical status on the 7 point ordinal scale would be 'not hospitalized, limitation on activities (b) 4-6 points' for a clinical status score for the participant on that day of 2.25.

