- The current signs and symptoms will be reviewed and the presence of symptoms sufficient to meet entry requirements will be confirmed. Entry Symptom Scale and Clinical Status to be recorded.
- A photo of the person's COVID-19 test result will be taken. If unavailable and the person opts to have the researchers request it, the person will provide signed permission Consent to Release Information and a photo will be taken of the document. This will permit researchers to obtain the test result document. Also, the person will be asked to sign the Consent to Release in case of hospitalization.

With confirmation of study eligibility:

- Vitals signs will be taken to include temperature, pulse, blood pressure, respiratory rate, and O₂ sat.
- Oro-pharyngeal swab will be obtained
- Blood draw for clinical safety labs and for research assays in quantity as specified in the Schedule of Events.
- The participant will be given a Symptoms log and instructed to daily take and record his/her own blood pressure and temperature. Temperature should also be taken whenever there is tactile fever. The participant will be provided with a digital thermometer and BP monitor as needed and instructed in their use. The participant will be asked to call *immediately* if systolic blood pressure falls below 90 mmHg and to NOT take further study medications unless advised by the study team that it is safe to do so.
- The pharmacist will randomize study participant to telmisartan or placebo; then the study medication will be dispensed to the participant. Participant will be instructed to take first dose as soon as he or she is home.
- Provide the following instructions to participants:
 - Take BP daily at generally the same time of the day and record on Symptoms log. Call research team if SBP is <90 and do not take further study medication unless instructed to do so by the research team.
 - Take temperature whenever a fever is suspected but at least once daily and record
 - Record appropriate fever, dyspnea and fatigue symptoms daily
 - Record the time study medication is taken daily
 - Participants will be advised to take particular effort to remain hydrated, and to be judicious with the use of aspirin or other NSAIDS for fever/symptomatic treatment because it may increase risk for renal problems if excessive amounts are taken with study medication.

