6.4.11 SCHEDULE OF EVENTS TABLE

Schedule of Events	Phone Screen	Entry (Day 1)	Day 4	Day 10	Day 21
Review COVID-19 symptoms and date of COVID-19 testing; Obtain Demographics, verbal Ht and Wt and Co-Morbid Medical History; Obtain Verbal Informed Consent	x				
Update current illness and confirm eligibility for study; verify signing of Informed Consent		x			
Complete Symptom Scale and Clinical Status		x	x	x	x
Vital Signs (Temp, Pulse, BP, Resp Rate, O ₂ sat)		x	x	x	x
Pregnancy test (except in post-menopausal state)		x	x*	x*	x*
Oro-pharyngeal Swab		x	x	x	x
Safety Labs (CBC with diff, chem, hsCRP, LDH) [10 ml]		x	x	x	x
RESEARCH Bloods including for RAS assessment (volume to be drawn) [25 ml]		x	x	x	x
TOTAL BLOOD VOLUME (ml)		35	35	35	35

*If possibility of pregnancy is solicited from participant

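### The primary proportional-odds model names no baseline covariate; prespecify the day 1 Symptom Scale total as its single covariate, whatever the observed balance

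*Combined protocol and SAP*

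**What the plan says.** Section 9.3.2 states: "The primary efficacy analysis will be performed using a proportional odds model". The treatment effect is tested one-sided, and no baseline covariate is listed. A second paragraph adds, as a supplement, a "generalized mixed-effect regression model (i.e., cumulative link mixed model) that contains treatment and days, and treatment: days interaction as fixed effects", fitted to days 1, 4, 10 and 21. That paragraph ends: "The regression models used for analysis can be further adjusted for any unbalanced covariates observed at baseline".

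Section 9.3.1 adds two statements: "A block randomization will be applied to ensure the balance of participant numbers and baseline severity between treatments" and "The covariate use in regression models will be limited due to the relatively small sample size". Neither 9.3.1 nor 9.5.1 names a severity factor or cut-point. Section 9.3.6 plans between-arm tests of baseline variables but attaches no decision to them.

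A suitable baseline measure exists. At the entry visit (6.4.6) the instruction is "Entry Symptom Scale and Clinical Status to be recorded", and the Schedule of Events (6.4.11) lists "Complete Symptom Scale and Clinical Status" on day 1. The first dose is taken at home after that visit. The same scale grades the endpoint category "Not hospitalized, limitation on activities as assessed by the Symptom Scale below" into levels 2.0 to 2.75 (4.1.1). For non-hospitalised participants the outcome window opens on day 3.

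For biomarkers at days 4, 10 and 21, section 9.3.3 plans a raw two-sample t-test or Wilcoxon test, with covariate adjustment only if needed. Mixed models that use day 1 values are additional.

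**The concern.** The plan treats entry severity as important: it wants it balanced at randomisation and gives it as an example subgroup factor in 9.3.8. Yet the primary model leaves it out, and the only route to including it depends on seeing an imbalance first. With 20 per arm, chance differences in entry severity are common unless the list controls them. A prognostic covariate fixed in advance recovers power and removes the effect of such differences. A covariate brought in only after an imbalance is seen does this poorly and leaves room for a data-dependent choice.

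Section 9.4 makes the Symptom Scale a natural candidate. Its assumptions put about 35 of the 40 outcomes in categories 1 and 2, and this scale subdivides category 2.

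**Working it through.** **Inputs.** From 9.4: 20 per arm, odds ratio 5, placebo probabilities 0.40, 0.40, 0.05, 0.04, 0.04, 0.04, 0.03. From 9.3.1 and 9.3.2: 5%, one-sided. The telmisartan vector in 9.4 has six entries summing to 0.99, so odds ratio 5 was applied to the placebo vector instead. This gives 0.769, 0.183, 0.014, 0.010, 0.009, 0.009, 0.006.

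**The plan's own figure.** Whitehead's formula is power = Φ(ln OR × √[(N/12)(1 − Σp̄³)] − z). The averaged probabilities give Σp̄³ = 0.225, so √[(40/12) × 0.775] = 1.608 and ln 5 × 1.608 = 2.587. One-sided 5%: Φ(2.587 − 1.645) = 82.7%. Two-sided 5%: Φ(2.587 − 1.960) = 73.5%. Simulation of the one-sided test gives 79.9% (Wald) and 81.6% (likelihood ratio). The stated figure of about 80% is therefore that of the unadjusted one-sided test.

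**Where outcomes fall.** Categories 1 and 2: 20 × 0.80 + 20 × 20/21 = 16 + 19.0 = 35.0 of 40.

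**Effect of adjusting.** The documents give no prognostic strength, so slopes of 0, 0.5, 1.0 and 1.5 log-odds per SD are assumed. These explain b²/(b² + π²/3) = 0, 7, 23 and 41% of latent variance. Tests are one-sided 5% likelihood-ratio tests. In the first three rows the marginal odds ratio is held at 5, with conditional odds ratios of 5.0, 5.4, 6.7 and 9.0 in the first row.

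| Setting | Unadjusted power, % | Adjusted power, % |
|---|---|---|
| Seven categories, no severity strata assumed | 81 / 81 / 82 / 81 | 81 / 83 / 88 / 92 |
| List stratified at the median score, blocks of 4 (assumed) | 82 / 81 / 82 / 84 | 82 / 83 / 87 / 93 |
| 12-level endpoint of 4.1.1, integer score (category splits assumed) | 83 / 83 / 83 / 82 | 83 / 84 / 89 / 94 |
| Seven categories, conditional odds ratio held at 5 | 80 / 78 / 70 / 61 | 80 / 80 / 77 / 77 |

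At slope 0 the unrounded loss in the last row is 80.1 − 79.7 = 0.4 point. A further independently coded simulation of the marginal case gave 80 to 79% at slope 0, 82 to 86% at slope 1.0 and 84 to 95% at slope 1.5, so read these figures as good to a point or two.

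**Type I error.** In the first row it is 5.3 to 5.7% unadjusted and 5.7 to 6.0% adjusted. On 12 levels it is 5.5 to 6.0% and 5.8 to 6.2%. With a stratified list whose strata the model ignores, the unadjusted test becomes conservative: 5.3, 5.2, 4.3 and 3.3%.

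**Chance imbalance.** Without strata, P(|difference| > 0.3 SD) = 2Φ(−0.3/√0.1) = 34%, or 17% in each direction. With the assumed strata it is 13% in total. Without strata, in the 17% of trials where telmisartan starts sicker by at least that much, power at slopes 0.5, 1.0 and 1.5 is 72, 61 and 55% unadjusted and 83, 86 and 92% adjusted.

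**Adjusting only after a significant baseline test.** With the conditional odds ratio at 5 and slope 1.0, adjusting only if the baseline t-test has p < 0.05 gives 70.4% power, against 77.4% for the prespecified covariate.

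**Binary fallback at odds ratio 5.** Category 1 versus 2 or higher: 20 × 0.60 + 20 × 0.231 = 12 + 4.6 = 16.6 events. Hospitalised or worse: 20 × 0.20 + 20/21 = 4 + 0.95 = 4.95 events.

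**Biomarkers at the d = 0.9 of 9.4, two-sided 5%.** The t-test has noncentrality 0.9 × √10 = 2.846 on 38 df, giving 79% power. ANCOVA has noncentrality 2.846/√(1 − r²) on 37 df, giving 83, 89 and 97% at assumed baseline correlations of 0.3, 0.5 and 0.7.

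**The case against.** The strongest reply is that nothing here is invalid. This is a feasibility-sized pilot, 9.3.1 deliberately limits covariates, and the unadjusted test holds its level. The gain depends on a slope the documents do not give. Entry requires symptoms and excludes people needing immediate admission, which narrows the score. Section 2.1 names age and co-morbidities as prognostic, not entry symptoms. The adjusted likelihood-ratio test is slightly the more liberal of the two. All of this stands, and it is why the size is a range that starts at a small loss. It does not undo the recommendation, because one covariate respects the limit and costs little if it proves useless.

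Four stronger readings are tempting, and the documents do not support them.

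- *The primary model is left open until baseline data are seen.* This holds only if the imbalance sentence covers the primary model. It closes the paragraph on the supplementary mixed model. Its wording is general, so the wider reading is plausible but not established.
- *The rule inflates type I error.* Reporting the better of the unadjusted and one-covariate results would give 6.0 to 8.8% (slopes 0 to 2.0), and the best of the unadjusted and five single-covariate models 9.8%. Nothing in the plan proposes such selection. A mechanical rule based on baseline p < 0.05 gives 4.4 to 5.5%.
- *False positives reach 10 to 20%.* Those rates (10, 15 and 20% at slopes 0.5, 1.0 and 1.5) apply only to the 17% of trials in which telmisartan starts milder by at least 0.3 SD, with no severity strata assumed.
- *Randomisation is not stratified.* Section 9.3.1 says the blocks balance severity. The factor is not named there or in 9.5.1, which does not show that it is absent.

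**Conclusion.** The point holds as a loss of efficiency and of protection against chance imbalance in a valid analysis. Adjusting for the day 1 total costs about 0.5 point of power if the scale is not prognostic. It gains 0 to 2 points at slopes up to 0.5, about 5 to 7 at 1.0 and about 9 to 12 at 1.5 with the marginal odds ratio held at 5. The gain is similar if the list is stratified by severity.

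The absolute adjusted power of 87 to 94% at slopes 1.0 and 1.5 rests on conditional odds ratios well above 5. With the conditional odds ratio held at 5, the gain is similar (larger at slope 1.5), but adjusted power stays at about 77 to 80%. All of this rests on assumed slopes and a proportional-odds effect. The biomarker gains likewise rest on assumed correlations, and the planned mixed models already use day 1 values.

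The change is worth making because the likely gain far exceeds the possible loss.

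**What to change.** In 9.3.2:

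- Prespecify the day 1 Symptom Scale total (0 to 12, linear) as the single covariate of the primary proportional-odds model, whatever the observed balance.
- State that the rule on unbalanced covariates does not apply to the primary analysis.
- Report the odds ratio as conditional on entry severity.
- If the randomisation list is stratified by severity, name the factor and have the model reflect it.
- In the binary fallback, keep the covariate when the cut leaves enough events, such as category 1 versus 2 or higher (about 17 expected at odds ratio 5). Use an unadjusted or exact comparison only for a sparse cut such as hospitalisation (about 5 expected). Fix the choice before unblinding.

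In 9.3.3, replace the raw two-sample tests at days 4, 10 and 21 with ANCOVA on the day 1 value, transformed where needed, alongside the planned mixed models.

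The cost is SAP wording; the data are already collected. The price is one degree of freedom, a conditional estimand, and a likelihood-ratio test that runs at about 6% with 40 participants. A re-randomisation check of the primary p-value is an optional safeguard.
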